### Study Interventions

Study protocol determines only the choice of intravenous isotonic crystalloid: 0.9% sodium chloride (saline group) versus the treating clinician's preference of Lactated Ringer's solution or Plasma-Lyte A® (balanced crystalloid group). Composition of each crystalloid solution is displayed in Table E1. Lactated Ringer's and Plasma-Lyte A® are the balanced crystalloids commonly available in the United States[20]. Lactated Ringer's and Plasma-Lyte A® both offer a significantly lower chloride content than saline, but other minor differences in composition lead some clinicians to prefer one balanced crystalloid or the other for particular patients (e.g., some clinicians prefer Plasma-Lyte A® over Lactated Ringer's for patients receiving blood transfusion)[21]. Allowing clinicians to select either Lactated Ringer's or Plasma-Lyte A® when a balanced crystalloid is assigned is anticipated to improve compliance

with balanced crystalloid assignment and emulate how balanced crystalloids are used in practice while maintaining relevant comparator groups consisting of crystalloid with a higher chloride content (saline) versus crystalloids with a lower chloride content (Lactated Ringer's and Plasma-Lyte A®). Decisions regarding crystalloid rate, volume, and additive content are deferred to treating clinicians.

Delivery of the assigned crystalloid to patients occurs via interventions in pharmacy supply and clinician order entry. Each month, the dispensing cabinets within the ICUs are stocked with 1000-mL bags of the assigned crystalloid. Additionally, any order for intravenous crystalloid for a patient located in a study ICU triggers an advisor application within the electronic order entry system. The advisor application informs providers about the study, asks about relative contraindications to the assigned crystalloid, and (if relative contraindications are not present) guides providers to order the assigned crystalloid. Accepted relative contraindications for patients assigned to balanced crystalloid include (1) "hyperkalemia" and (2) "brain injury". The severity of "hyperkalemia" and "brain injury" at which saline will be used in favor of balanced crystalloids is determined by the treating clinician. The non-assigned crystalloid is also made available via the pharmacy if a formal statement is submitted that the attending physician feels the non-assigned crystalloid is required for the safe treatment of a specific patient.

Although the study focuses on crystalloid use in the ICU, crystalloid administration prior to ICU admission in the emergency department or operating room may introduce contamination and limit separation between study arms. Therefore, between January 1, 2016 and April 30, 2017, the Vanderbilt University Medical Center Emergency Department (ED) is coordinating their crystalloid use with the medical, surgical, and trauma ICUs such that patients admitted to those units from the ED begin receiving the assigned crystalloid during evaluation and management in the ED (NCT02614040). Clinical outcomes of patients treated with study crystalloids in the ED and hospitalized outside the ICU will be recorded and reported separately. Similarly, to the extent that is logistically feasible, for patients identified in the operating room as coming from or being admitted to one of the participating ICUs, the request is made that they receive the fluid assigned to the corresponding ICU during their operative

procedure. Fluid administered prior to enrollment by the emergency medical system and outside hospitals, and fluid administered after discharge from the ICU, is not controlled by the study.

Each day patients receive the crystalloid to which their ICU is currently assigned. The necessity that an intravenous crystalloid be clinically available at all times precluded the use of washout periods and patients who remain in the ICU through a crossover (i.e., from one calendar month to another) may potentially be exposed to both types of crystalloid. Although this introduces the potential for contamination of study groups, in a pilot trial at the same institution, the total volume of non-assigned crystalloid administered due to the lack of a washout period was less than 125 mL per patient[14]. As described in the *Statistical Analysis* section below, patients will be analyzed in the group to which they were assigned at the time of study enrollment in an intention-to-treat fashion (e.g., a patient admitted to an ICU during a month assigned to saline will be analyzed in the saline group even if that patient remains in the ICU after the ICU switches assignment to balanced crystalloids).

## Data Collection

This pragmatic trial uses data collected via routine clinical care and electronically extracted from the electronic health record (EHR). All data are stored confidentially in an institutional patient data management system. Data collected include: pre-study renal function; demographic characteristics, admitting location and diagnosis, and severity of illness at enrollment; receipt of intravenous crystalloids, other fluids, and blood products; serum electrolyte and creatinine values; receipt of RRT, mechanical ventilation, and vasopressors; and vital status and serum creatinine at hospital discharge. Electronic extraction of these data from the EHR has been previously validated against the reference standard of two-physician manual chart review[22]. For all patients who receive new RRT, study personnel will perform manual chart review to confirm the absence of prior RRT and identify the indication for RRT.

## Primary Outcome

The primary outcome will be the proportion of patients meeting one or more criteria for Major Adverse Kidney Events within the 30 days after enrollment (MAKE30): in-hospital mortality, receipt of new RRT, or persistent renal dysfunction defined as a final inpatient serum creatinine value  $\geq 200\%$  of baseline[22–24]. In-hospital mortality will be defined as death from any cause prior to hospital discharge censored at 30 days after ICU admission. Receipt of new RRT will be defined as receipt of any modality of RRT between ICU admission and the first of hospital discharge or 30 days, among patients not known to have received RRT prior to ICU admission. Persistent renal dysfunction will be defined as a final serum creatinine value before hospital discharge (censored at 30 days after enrollment)  $\geq 200\%$  of the baseline creatinine value. The value for baseline serum creatinine will be determined using a previously-described hierarchical approach[22]. The lowest serum creatinine between 12 months and 24 h prior to hospital admission will be used when available. If no such creatinine value is available, the lowest creatinine value between 24 h prior to hospital admission and the time of ICU admission will be used. If no creatinine value is available between 12 months prior to hospital admission and the time of ICU admission, a baseline creatinine value will be estimated using a previously-described formula [creatinine =  $0.74 - 0.2$  (if female) +  $0.08$  (if African American) +  $0.003 \times$  age (in years)][25]. Patients known to have received RRT prior to enrollment will be considered ineligible to meet criteria for new RRT or persistent renal dysfunction, but may qualify for MAKE30 by experiencing in-hospital mortality.

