## Additional Secondary Analyses

We will perform the following additional secondary analyses:

- (1) Comparison of secondary outcomes between study groups.
- (2) Effect modification by severity of illness and pre-specified subgroups. Using generalized linear mixed effects modeling, we will examine the interaction between crystalloid assignment and the following baseline variables with respect to the primary outcome of MAKE30 in the intention-to-treat population:

- a. Source of admission to the ICU (Emergency department, Operating room, Transfer from another hospital, Hospital ward, Other)
- b. Study ICU (Medical, Surgical, Cardiac, Neurological, Trauma). [Because cluster cannot be treated as a random effect for this subgroup, we will use logistic regression modeling]
- c. Sepsis or septic shock (Yes, No)
- d. Traumatic brain injury (Yes, No)
- e. Receipt of mechanical ventilation (Yes, No)
- f. Receipt of vasopressors (Yes, No)
- g. Category of renal dysfunction at the time of enrollment (No renal dysfunction, Acute kidney injury, Chronic kidney disease, End-stage renal disease receiving RRT)
- h. Risk of in-hospital mortality as predicted by baseline University HealthSystem Consortium expected in-hospital mortality (continuous variable ranging 0.0 to 1.0)

(3) Sensitivity analysis excluding patients admitted in the week prior to a crossover ('washout'). We will repeat the primary analysis comparing MAKE30 between study groups in the intention to treat population excluding those admitted in the 7 days prior to a crossover in ICU crystalloid assignment (simulating a "washout" period). Prior data from the study ICUs suggests that less than 10% of patients remain in the ICU for longer than 7 days[14]. Excluding those admitted within 7 days of a crossover in ICU crystalloid assignment will allow use of a baseline factor to exclude the majority of patients who would go on to experience a crossover in crystalloid assignment due to the study design.

(4) Sensitivity analysis excluding patients who were transferred between ICUs or remained in the ICU through a crossover ('per protocol'). We will repeat the primary analysis comparing MAKE30 between study groups in the intention to treat population excluding those who remained in the intensive care unit through a crossover in crystalloid assignment or were transferred between study ICUs.

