### **Handling of Missing Data**

Of the components of the MAKE30 primary outcome, data regarding in-hospital mortality and receipt of new renal replacement therapy are not anticipated to be missing for any patients[14,22]. In contrast, the persistent renal dysfunction component of MAKE30 may suffer from missing data for serum creatinine value at baseline or between enrollment and hospital discharge. In a pilot study of 974 patients in the same hospital, 31 patients (3.2%) had no measured serum creatinine between enrollment and hospital discharge[14]. Of these 31 patients, 6 (19.4%) died within hours of ICU admission and qualified for the MAKE30 outcome via the in-hospital mortality criteria. The remaining 25 (80.6%) were low acuity ICU patients with a normal creatinine value measured in the 24 hours prior to ICU admission who were discharged from the hospital within 48 hours without another serum creatinine measurement. Of these, 24 had a subsequent outpatient serum creatinine value measured in the next 90 days, all of which were in the normal range. Thus, patients without a serum creatinine measurement between enrollment and hospital discharge, who do not experience in-hospital mortality or new RRT, will be classified as having not experienced the MAKE30 outcome.

With regard to missing data for baseline serum creatinine, in the same pilot study 595 of 974 patients (61.0%) had a measured serum creatinine value between 12 months and 24 hours prior to hospital admission[14]. Of those without such a measurement, 259 of 379 (68.3%) had a value measured between 24 hours prior to hospital admission and study enrollment. Only 120 of 974 patients (12.3%) did not have an available serum creatinine value prior to enrollment. For the main analysis, patients without a measured serum creatinine value between 12 months prior to hospital

admission and enrollment will have a baseline creatinine value estimated using a previously-described three-variable formula[29]. Multiple alternative approaches to missing baseline creatinine data will be explored in sensitivity analyses including use of complete cases, multivariable single imputation, and use of the first creatinine after enrollment or the highest or lowest creatinine during the study (see Appendix 5).

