**Table E2. Elixhauser comorbidity index.**

	Saline	Balanced
Comorbidity, No. (%)	(n = )	(n = )
Congestive heart failure	--	--
Cardiac arrhythmias	--	--
Valvular disease	--	--
Pulmonary circulation disorders	--	--
Hypertension, uncomplicated	--	--
Hypertension, complicated	--	--
Paralysis	--	--
Other neurological disorders	--	--
Chronic pulmonary disease	--	--
Diabetes, uncomplicated	--	--
Diabetes, complicated	--	--
Hypothyroidism	--	--
Renal failure	--	--
Liver disease	--	--
Peptic ulcer disease excluding bleeding	--	--
Acquired immunodeficiency syndrome	--	--
Lymphoma	--	--
Metastatic cancer	--	--
Solid tumor without metastasis	--	--
Rheumatoid arthritis / collagen vascular disease	--	--
Coagulopathy	--	--
Obesity	--	--
Weight loss	--	--
Fluid and electrolyte disorders	--	--
Blood loss anemia	--	--
Deficiency anemias	--	--
Alcohol abuse	--	--
Drug abuse	--	--
Psychoses	--	--
Depression	--	--

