### **Renal Function**

**Baseline serum creatinine** – The value for baseline serum creatinine will be determined in a hierarchical approach. The lowest serum creatinine between 12 months

and 24 h prior to hospital admission will be used when available. If no such creatinine value is available, the lowest creatinine value between 24 h prior to hospital admission and the time of ICU admission will be used. If no creatinine value is available between 12 months prior to hospital admission and the time of ICU admission, a baseline creatinine value will be estimated using a previously-described three-variable formula [creatinine = 0.74 – 0.2 (if female) + 0.08 (if African American) + 0.003 × age (in years)][25].

**Acute kidney injury, stage II or greater** – Stage II or greater acute kidney injury will be defined according to Kidney Disease Improving Global Outcomes (KDIGO) creatinine criteria[26] as a creatinine value between enrollment and the first of hospital discharge or 30 days at least 200% of the baseline value OR both (1) greater than 4.0 mg/dL and (2) increased at least 0.3 mg/dL from baseline. Patients may have acute kidney injury present at the time of first creatinine measurement after enrollment (prevalent AKI) or acute kidney injury developing during the study (incident AKI). Incident AKI will be defined as any creatinine value between enrollment and discharge or 30 days that is (1) increased at least 0.3 mg/dL from a preceding post-enrollment value AND (2) at least 200% of the baseline value, at least 200% of a preceding post-enrollment value, or at least 4.0 mg/dL.

**Chronic kidney disease stage III or greater** – Chronic kidney disease stage III or greater will be defined as a glomerular filtration rate less than 60 ml/min per 1.73 m^2 as calculated by the Chronic Kidney Disease Epidemiology (CKD-EPI) Collaboration equation[33] using the patient's baseline creatinine value.

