## Appendix 5: Handling of Missing Baseline Serum Creatinine Values

For patients without a measured serum creatinine between 12 months prior to hospital admission and enrollment, baseline creatinine value for the primary analysis will be estimated using a previously-described three-variable formula [creatinine = 0.74 – 0.2 (if female) + 0.08 (if African American) + 0.003 × age (in years)][25]. Multiple sensitivity analyses will employ alternative approaches to estimating missing baseline creatinine values:

- 1) A ‘complete cases’ analysis will be performed in which patients without a measured creatinine value between 12 months prior to hospital admission and enrollment will be excluded.
- 2) Missing baseline serum creatinine values will be imputed by multivariable single imputation using the R function `aregImpute` in `Hmisc` package with 5 imputations. The imputation model will include age, gender, race, group assignment, source of admission, primary diagnosis, receipt of mechanical ventilation, vasopressor receipt, prior hemodialysis, total fluids received in 30 days, UHC expected mortality, overall mortality, new RRT received, minimum creatinine value, maximum creatinine value, and final study creatinine value. Continuous variables will be transformed via cubic splines with 3 to 5 knots.
- 3) Simple imputation will be performed in which first serum creatinine value after enrollment is used as the baseline creatinine.
- 4) Simple imputation will be performed in which the highest serum creatinine value between enrollment and 30 days is used as the baseline creatinine.
- 5) Simple imputation will be performed in which the lowest serum creatinine value between enrollment and 30 days is used as the baseline creatinine.

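### CKD stage III is derived from the baseline creatinine even when that baseline is an age, sex and race formula, so essentially no patient on a formula baseline can be classed as CKD in Table 1 or, by the only definition given, in the renal-dysfunction subgroup

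*Combined protocol and SAP*

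**What the plan says.** The SAP (Primary Outcome, repeated in Appendix 2, Renal Function) sets the baseline creatinine in three steps. The first choice is the lowest value from 12 months to 24 hours before hospital admission. Failing that, "the lowest creatinine value between 24 h prior to hospital admission and the time of ICU admission will be used". The third step applies "If no creatinine value is available between 12 months prior to hospital admission and the time of ICU admission". In that case the SAP turns to an equation with sex, race and age as its only inputs; in its words, "a baseline creatinine value will be estimated using a previously-described formula". Handling of Missing Data gives the pilot experience: "Only 120 of 974 patients (12.3%) did not have an available serum creatinine value prior to enrollment".

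Appendix 2 then states: "Chronic kidney disease stage III or greater will be defined as a glomerular filtration rate less than 60 ml/min". The rate is indexed to body surface area and comes from the CKD-EPI equation, applied to the study baseline. Appendix 2 makes no distinction between a measured and an estimated baseline.

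This classification has its own row in Table 1. Additional Secondary Analyses, item (2) g, tests effect modification by "Category of renal dysfunction at the time of enrollment (No renal dysfunction, Acute kidney injury, Chronic kidney disease" and a fourth level for end-stage disease on RRT. The SAP does not say how patients are assigned to these levels, and Appendix 2 holds its only definition of CKD.

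Other information on prior kidney disease is collected. Table E2 lists "Renal failure" among the Elixhauser comorbidities, and section 8.4.1 of the final protocol (6/15/17) collects ICD diagnoses. Neither enters the baseline rule or the CKD definition.

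**The concern.** A baseline built from age, sex and race says nothing about whether the patient had kidney disease before admission. Using it to decide who has CKD settles the answer in advance: the formula returns a typical healthy value, and the CKD rule reads that value as healthy kidneys.

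The Table 1 row would then understate CKD. In the subgroup analysis, CKD patients without a prior creatinine would sit in the wrong strata, and the CKD stratum would hold only those with a measured value. Effect modification by baseline renal function is a natural question in a trial with a kidney outcome, and strata mixed in this way blur any difference between them.

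**Working it through.** **1. How many patients are on the formula.** Inputs are the pilot counts in Handling of Missing Data. Without a value in the 12-month window: 974 − 595 = 379. Of these, 259 had a later value before enrollment: 379 − 259 = 120. Then 120/974 = 12.3%, which reproduces the plan's figure (binomial 95% interval 10.3% to 14.4%). Applied to 14,000 patients this is about 1,725. Applied to the 15,000 to 16,500 in the final protocol's Final Anticipated Sample Size it is about 1,850 to 2,030.

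**2. What the formula returns.** Baseline = 0.74 − 0.2 (woman) + 0.08 (African American) + 0.003 × age.

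- Lowest at ages 18 to 90 (woman, not African American, 18): 0.74 − 0.2 + 0.054 = 0.594 mg/dL.
- Highest (African American man, 90): 0.74 + 0.08 + 0.27 = 1.09 mg/dL.

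**3. What the CKD rule makes of it.** The documents cite CKD-EPI but do not print its coefficients, so I assume the 2009 form: 141 × min(Cr/κ, 1)^α × max(Cr/κ, 1)^−1.209 × 0.993^age × 1.018 (woman) × 1.159 (African American), with κ = 0.7 and α = −0.329 for women, κ = 0.9 and α = −0.411 for men.

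| Group | Formula value, age 60 | eGFR, age 60 | Formula value, age 90 | eGFR, age 90 | First age with eGFR < 60 |
|---|---|---|---|---|---|
| Man, not African American | 0.92 | 90.1 | 1.01 | 65.2 | 98 |
| Woman, not African American | 0.72 | 91.0 | 0.81 | 63.9 | 96 |
| African American man | 1.00 | 94.4 | 1.09 | 68.9 | 104 |
| African American woman | 0.80 | 92.9 | 0.89 | 66.1 | 99 |

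The lowest eGFR at ages 18 to 90 is 141 × (0.81/0.7)^−1.209 × 0.993^90 × 1.018 = 141 × 0.838 × 0.531 × 1.018 = 63.9. Below age 96 no formula value can give CKD stage III. The coefficients set these exact ages. The lack of information on prior kidney disease does not depend on them.

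**4. Where a true CKD patient lands.** Take a man of 60, not African American, with a steady creatinine and no earlier value. His formula baseline is 0.92, and twice that is 1.84. An eGFR of 60 corresponds to about 1.29 mg/dL.

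- Steady at 1.30 to 1.83 (eGFR about 59 to 39): true stage III, but below 200% of baseline, so he is labelled as having no renal dysfunction.
- Steady at 1.84 or more (eGFR 39 or less): at least 200% of baseline, so he meets the Appendix 2 rule for stage II AKI at his first measurement and is labelled AKI.

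**5. How many are mislabelled.** The documents do not give the share of formula patients with CKD not on RRT. If it is 5%, 10% or 20% (assumed), then 1,725 × share = about 86, 172 or 345 of 14,000, that is 0.6%, 1.2% or 2.5% of the trial.

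**6. The primary outcome.** The patient steady at 1.84 or more also meets persistent renal dysfunction. The plan's power reproduces: 7,000 per group at 15.0% versus 13.1%, two-sided 0.05, gives 89.9%. Suppose a share s of formula patients scored falsely in both groups, on top of those rates. With s = 5%, q = 0.1232 × 0.05 = 0.0062, and the rates become 0.150 + 0.85q = 15.5% and 0.131 + 0.869q = 13.6%, with power 88.6%. With s = 20% power is 84.6%. Both values of s are assumptions.

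**7. Appendix 5 against step 6.** Item 4 takes the highest post-enrollment creatinine as baseline. The final value cannot be twice the highest, so under item 4 every formula patient can meet MAKE30 only by death or new RRT, and nobody is dropped. Under items 3 (first value) and 5 (lowest value) a steady creatinine has a ratio of about 1 and is not an event.

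**The case against.** The strongest reply is that little depends on this. It touches one descriptive row and one level of a subgroup analysis that the SAP itself calls hypothesis-generating. Table 1 reports how many patients have a formula baseline, so a reader can see the extent. The link from subgroup (g) to the Appendix 2 definition is an inference: the SAP does not state how the levels are assigned, and the R code is in an additional file not available here. All of this stands, and it limits the weight of the point. It does not make the rule right, because Appendix 2 as written gives a wrong label and no other definition is offered.

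A reader might go further and infer that stable CKD is generally counted as a MAKE30 event. The documents do not support that. It scores only at or above twice the formula value, about 1.4 to 2.0 mg/dL at age 60, so milder stage III at that age does not score. Prior-RRT patients cannot score on creatinine. Patients with no post-enrollment creatinine are non-events unless they die or receive RRT. The rule is the same in both groups, so no bias toward either fluid is shown. Nor is a power shortfall shown: the 15% rate came from the study ICUs' own prior-year data, collected with the same variables, and plausibly already contains such events.

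A reader might also take 12.3% as the share with missed CKD. It is the share given the formula in one pilot, and the five ICUs together may differ.

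**Conclusion.** The point holds for CKD classification. Under Appendix 2 as written, essentially every patient on a formula baseline is recorded as free of CKD. The pilot puts 12.3% of patients in this position, about 1,725 of 14,000. The number actually mislabelled is the unknown part of these who have CKD not treated by RRT. The effect on Table 1 is certain in kind; the effect on subgroup (g) assumes that it uses the Appendix 2 definition.

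It does not extend to a fault in the primary outcome. Stable CKD at or above twice the formula value adds noise of unknown size and no particular direction, and Appendix 5 items 3 to 5 already test for it. No further sensitivity analysis is required. None of the five Appendix 5 analyses is stated to redo the CKD classification, so that part remains open.

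**What to change.** In Appendix 2 (Renal Function), state that CKD stage III or greater is derived only from a measured baseline creatinine. In Table 1 and subgroup (g), place patients with an estimated baseline in a separate level for unknown baseline. Patients with prior RRT stay in the end-stage level, which does not depend on creatinine. State in the SAP how each level of subgroup (g) is assigned.

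An alternative is to class formula patients as CKD from a recorded diagnosis, provided it denotes chronic disease. The documents do not show that the Elixhauser entry "Renal failure" excludes acute failure during the index stay. If it does not, using it would label AKI as CKD, so the separate level is the safer default.

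The cost is a few sentences and lines of code on data already collected, one more category, and a somewhat smaller classified population, by about 12% if the pilot share holds. A diagnosis-based version also carries imperfect coding. The MAKE30 definition and the Appendix 5 list stay as they are. The change should be written into the SAP, because its closing section treats any analysis not contained in it as post hoc.
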